6.3.1.2 Missing Efficacy Data During the DBT Phase

Missing efficacy data during the DBT Phase are tabulated by treatment group as the number and percentage of subjects in the DBT efficacy analysis set in the following categories:

- Missing headache pain intensity at each time point from 15 minutes through 48 hours postdose. These categories are not mutually exclusive because subjects may have missing headache pain intensity at multiple time points.
- Number of time points with missing migraine headache pain intensity from 2 hours to 48 hours postdose: 0 (i.e., no missing migraine headache pain intensity), 1, 2, 3, 4, 5, 6, 7. These categories are mutually exclusive.

- Missing data for the following efficacy parameters at 2, 24, and 48 hours postdose: migraine headache pain intensity, nausea status, phonophobia status, photophobia status, and functional disability level.

6.3.2 Primary Efficacy Endpoint: Pain Relief at 2 Hours Postdose During the DBT Phase

The primary efficacy endpoint is evaluated for the DBT efficacy analysis set.

Pain relief at a single time point postdose is defined as having a headache pain intensity of none or mild at that time point.

6.3.2.1 Primary Efficacy Endpoint: Main Analysis

The percentage of subjects with pain relief at 2 hours postdose during the DBT Phase is compared between treatment groups using Mantel-Haenszel risk estimation (e.g., SAS proc `stdrate`) with stratification by history of clinically relevant CV disease randomization stratum (yes or no). In these analyses, the NC=F and RM=F methods are applied (see Section 6.3.5.1). The following statistics are presented:

- Response rate (i.e., “n/N” and percentage), ASE, and 95% CI for each treatment group
- Stratified percentage difference between treatment groups (rimegepant – placebo), ASE, 95% CI, and p-value.

These results are presented together in the same table as those for pain relief over time during the DBT Phase (see Section 6.3.5.1).

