- In the OLE Phase, lasting up to 12 weeks, subjects will be able to take up to 1 tablet of open-label study drug (75 mg ODT rimegepant) per calendar day as needed for acute treatment of migraine for a maximum of 18 doses per month (month is 28 days).
 - ***During the OLE Phase***
 - Subjects are to use open-label study drug as the first treatment of migraine attacks of moderate or severe headache pain intensity, and should not take acute migraine medication before taking open-label study drug
 - In association with each of the ***First 5 Qualifying Migraine Attacks***, subjects are required to complete the MQoL Questionnaire within the eDiary at 24 hours after dosing with open-label study drug
 - If migraine-associated symptoms persist beyond 2 hours after dosing with open-label study drug, subjects may use permitted acute migraine medication for the purposes of rescue, as needed and in accordance with the standard of care. *All dosing of rescue medication (permitted or exclusionary), is to be recorded on the Rescue Medication paper diary.*

Number of Subjects:

Approximately 600 subjects will be randomized in a 1:1 ratio to blinded rimegepant or matching placebo in the DBT Phase. Randomization will be stratified by history of clinically relevant cardiovascular (CV) disease (yes, no). In addition, randomization of subjects in the

CV subgroup (“yes” category) will be capped at 15%. In the OLE Phase, the study drug will be 75 mg ODT of open label rimegepant as needed, up to once per calendar day.

Study Population:

The study will recruit subjects ≥ 18 years of age with a minimum 1 year documented history of migraine attacks (with or without aura) consistent with a diagnosis according to the International Classification of Headache Disorders, 3rd Edition.

Per self-report, with confirmation from Investigator/ supporting medical record, subjects must have:

1. Migraine attacks present for more than 1 year with the age of onset prior to 50 years of age.
2. Migraine attacks, on average, lasting about 4 - 72 hours if untreated.
3. 4 to 14 migraine days per month on average across the 3 months prior to the Screening Visit (month is defined as 28 days for the purpose of this protocol).
4. Less than 15 headache days (migraine or non-migraine) per month in each of the 3 months prior to the Screening Visit and throughout the Screening Phase
5. Less than 7 non-migraine headache days per month, on-average, across the 3-months prior to the Screening Visit

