9.1. Sample Size

It is anticipated that about 90% of the 300 subjects randomized to each treatment group will have a migraine in the allotted time period of the DBT Phase, resulting in approximately 270 subjects evaluable for efficacy in each treatment group. The sample size calculation is based on pooled results from Phase 3 single-dose migraine studies BHV3000-301, BHV3000-302, and BHV3000-303. Pooled response rates for migraine headache pain relief at 2 hours postdose were 57.9% for rimegepant 75 mg and 43.9% for placebo in these studies.

A total sample size of 540 evaluable subjects (270 per treatment group) will provide approximately 90% power for the primary endpoint of migraine headache pain relief at 2 hours postdose in the DBT Phase. This is based on a chi-square test with a 2-sided alpha level of 0.05 and assumes that the true response rates in the subjects unsuitable for triptan use will be equivalent to the overall pooled response rates above.

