9.3.1.1. Primary Endpoint

Rimegepant will be tested for superiority against placebo at a 2-sided alpha level of 0.05 for the primary endpoint of migraine headache pain relief at 2 hours postdose during the DBT Phase using the DBT efficacy analysis set. Treatment groups will be compared using Mantel-Haenszel risk estimation with stratification by history of clinically relevant CV disease (yes, no), to estimate the difference in percentages of subjects achieving the endpoint response criteria (rimegepant – placebo). The percentage of subjects achieving the endpoint response criteria will be presented with a 95% confidence interval (CI) by treatment group. The

stratified difference in percentages between treatment groups will be presented with a 95% CI and p-value.

Subjects with missing data at 2 hours postdose will be classified as failures (i.e., Non-completer = Failure; NC=F).

Sensitivity analyses will be described in the SAP.

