6.3.2.2 Primary Efficacy Endpoint: Sensitivity Analyses

Sensitivity analyses of the primary efficacy endpoint (i.e., pain relief at 2 hours postdose during the DBT Phase) are provided in separate tables.

The RM=F method uses both criteria to classify subjects as failures (see Section 7.5).

Copy Reference Multiple Imputation

The main analysis is repeated using the copy reference multiple imputation approach with $n = 30$ imputations to impute missing headache pain intensity at 2 hours postdose. The fully conditional specification (FCS) method is used with a generalized logit distribution. Covariates may include history of clinically relevant CV disease randomization stratum (yes or no), sex, migraine headache pain intensity at the time of DB study drug dosing (moderate or severe), historical number of moderate to severe migraine attacks per month ($< \text{median}$, $\geq \text{median}$), MBS before DB study drug dosing (nausea, phonophobia, or photophobia), and geographic region (Australia/Europe or North America). First, the RM=F method of handling rescue medication use is applied. Next, missing response status (responder versus failure) in the 2-hour postdose analysis window is imputed for subjects who are not missing any of the covariates (subjects

missing any of the covariates are considered failures). The same statistics as the main analysis are presented, except “n/N”.

Varying Response Rate Imputation

The main analysis is repeated by imputing missing headache pain intensity at 2 hours postdose in each treatment group with varying response rates over the range of 0%, 10%, 20% and 30%. First, the RM=F method of handling rescue medication use is applied. Next, missing response status (responder versus failure) in the 2-hour postdose analysis window is imputed. The following statistics are presented: stratified percentage difference between treatment groups (rimegepant – placebo), ASE, 95% CI, and p-value.

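### The primary analysis is valid but stratifies only by CV history; adding pain intensity at dosing, recorded for every analysed subject, would gain precision if it is prognostic

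*SAP*

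**What the plan says.** - **Primary analysis.** SAP 6.3.2.1 uses Mantel-Haenszel risk estimation "with stratification by history of clinically relevant CV disease randomization stratum (yes or no"). Protocol 9.3.1.1 agrees: "with stratification by history of clinically relevant CV disease (yes, no"). SAP 6.3 uses the imputed CV stratum and allows an unstratified presentation when data in a stratum are sparse.
- **Outcome.** A responder has pain of none or mild at 2 hours on a four-point scale (SAP 3.2.1 and 6.3.2).
- **Availability of intensity.** The DBT efficacy set requires a qualifying attack at dosing (SAP 4.1). SAP 9.3.1 derives such an attack from an eDiary record of moderate or severe pain, so the value exists for everyone analysed.
- **Where intensity is used.** It is tabulated by randomized group (SAP 6.2.5 and 6.2.5.2). For the primary endpoint, SAP 6.3.2.2 names "migraine headache pain intensity at the time of DB study drug dosing (moderate or severe") as a possible covariate in the copy reference imputation model, after which the CV-stratified comparison is repeated. It is not an efficacy subgroup (SAP 4.3.1).

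**The concern.** Response means falling from moderate or severe to none or mild, so it is reasonable to expect attacks that start severe to respond less often. If they do, a comparison that ignores the starting level has a larger variance than one that uses it.

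Subjects are randomized at the Baseline Visit and treat an attack up to 45 days later (Protocol 4.3.2). The intensity of that attack is unknown at randomization, so it cannot be a randomization factor. Only the analysis can deal with an uneven split. No planned treatment comparison does so, and an adjustment chosen after unblinding would be post hoc.

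At stake are some precision on the primary endpoint and protection against chance imbalance. The validity of the test is not in question.

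**Working it through.** **Inputs from Protocol 9.1 (repeated in SAP 5)**
- Rates: "Pooled response rates for migraine headache pain relief at 2 hours postdose were 57.9% for rimegepant 75 mg and 43.9% for placebo", a difference of 0.140.
- Size: "A total sample size of 540 evaluable subjects (270 per treatment group) will provide approximately 90% power". It follows from the expectation that "about 90% of the 300 subjects randomized to each treatment group will have a migraine" (300 × 0.90 = 270).
- Test: "This is based on a chi-square test with a 2-sided alpha level of 0.05".

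**Inputs not in the documents (assumed)**
- q, the severe share at dosing: 20% to 50%. Because q(1−q) is symmetric about 50%, the same bounds cover shares up to 80%.
- g, response in moderate minus response in severe attacks: 0 to 30 points, taken as equal in both arms.

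**Step 1. Reproduce the stated power.** The mean rate is (0.579 + 0.439)/2 = 0.509.
- Null SE = √(2 × 0.509 × 0.491/270) = 0.0430.
- Alternative SE = √((0.579 × 0.421 + 0.439 × 0.561)/270) = √(0.4900/270) = 0.0426.
- Power = Φ((0.140 − 1.96 × 0.0430)/0.0426) = 90.4%. The stated figure of about 90% is confirmed.

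The unpooled version, which matches a risk difference with its own SE, is Φ(0.140/0.0426 − 1.96) = 90.8%, with a 95% CI half-width of 8.35 points. This is the reference below.

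**Step 2. Add intensity as a stratum.** With a common risk difference across strata, the within-arm variance p(1−p) becomes p(1−p) − q(1−q)g². The proportional reduction is 2q(1−q)g²/0.4900. For q = 0.30 and g = 0.20 it is 2 × 0.21 × 0.04/0.4900 = 3.4%.

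| Severe share | Gap (points) | Variance reduction | CI half-width (points) | Power |
|---|---|---|---|---|
| any | 0 | 0% | 8.35 | 90.8% |
| 30% | 10 | 0.9% | 8.31 | 91.0% |
| 30% | 20 | 3.4% | 8.21 | 91.7% |
| 30% | 30 | 7.7% | 8.02 | 92.8% |
| 20% | 30 | 5.9% | 8.10 | 92.3% |
| 50% | 30 | 9.2% | 7.96 | 93.2% |

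The third row is worth about 19 subjects (540/(1 − 0.0343) = 559).

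**Step 3. Simulation check.** This used 10,000 trials per setting, 540 subjects, 15% with CV history and the Sato variance. Monte Carlo error on power is about 0.3 points (√(0.9 × 0.1/10,000)).

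| Setting | CV only | CV × intensity |
|---|---|---|
| q 30%, g 0: power | 90.2% | 90.1% |
| q 30%, g 10: power | 91.0% | 90.9% |
| q 30%, g 20: power | 90.3% | 91.1% |
| q 40%, g 25: power | 90.6% | 92.2% |
| q 30%, g 20, no effect: rejection rate | 5.2% | 5.3% |

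At gaps of 10 points or less there is no visible gain in power. Type I error is essentially the same for both analyses.

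**Step 4. Chance imbalance.** The difference in severe share between arms has SD √(2q(1−q)/270), and it shifts the estimate by g times that difference.
- q = 30%, g = 20: 1.96 × 0.20 × √(0.42/270) = ±1.5 points.
- q = 50%, g = 30: 1.96 × 0.30 × √(0.50/270) = ±2.5 points.

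Both compare with an assumed effect of 14 points. This is part of the same variance as in Step 2, not an additional loss.

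**Step 5. Smallest stratum.** With CV history capped at 15% and 30% severe, the CV-yes/severe stratum holds at most about 540 × 0.15 × 0.30 = 24 subjects.

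**The case against.** The case for leaving the plan alone is solid in several respects.

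- **The analysis is sound as written.** It uses the only randomization factor, protocol and SAP agree, and the design reaches about 90% power on an unstratified test. This stands: the point concerns efficiency, not an error.
- **The gain is not documented.** It is nil if intensity is not prognostic, and the largest figures need an even split together with a 30-point gap. This stands, and the result should only be quoted as a range.
- **Intensity is not always recorded before dosing.** SAP 7.4.1.1 accepts retrospective dose entries. SAP 7.4.2 restricts the most bothersome symptom to collection before dosing but does not so restrict pain intensity. Some values may therefore be recalled after the tablet, possibly under its influence, and the documents give no count. This calls for a check but is no bar, since the same recorded value already decides entry to the efficacy set.
- **Four strata invite the sparse-data option.** Mantel-Haenszel tolerates the small stratum, as the simulated null rate shows. The open-ended option in SAP 6.3 does become likelier to be used, so it needs a fixed rule.
- **An imbalance would be visible.** True, but showing it in a baseline table does not correct the estimate.
- **The imputation model lists other covariates too.** Sex, attack frequency, most bothersome symptom and region are also named there. Intensity is singled out because it is the baseline of the outcome scale itself.

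**Conclusion.** The planned primary analysis is valid but omits the baseline level of its own outcome, a value available for every analysed subject. Under the assumed ranges, adding it lowers variance by 0% to 9.2% and raises unpooled power by 0 to about 2.4 points (93.2 − 90.8). At 30% severe and a 20-point gap, power rises by about 0.9 points. These figures assume the planning rates, 270 per arm and a common risk difference across strata.

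A reader might infer more than the documents support:
- That the planned intervals are known to be too wide. Without response by intensity, this cannot be said.
- That the SAP already treats intensity as prognostic. It lists intensity only as a covariate that may enter one sensitivity imputation model.
- That CV history was chosen for safety and is irrelevant to efficacy. Protocol Appendix 4 gives stratification and subgroup analysis as its purpose, and exploratory objective 17 covers efficacy as well as safety.
- That the same gain applies to the key secondary endpoints. The documents give no planning rates for them, and nothing was calculated.

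**What to change.** 1. While the study is still blinded (SAP 2.3 keeps it so through the PCD database lock), amend SAP 6.3.2.1 and Protocol 9.3.1.1. Define the Mantel-Haenszel strata as CV history (yes/no) by headache pain intensity at dosing (moderate/severe). Apply them to the primary endpoint and to the pain-based key secondary endpoints (SAP 6.3.3.1 and 6.3.3.6 to 6.3.3.9).
2. Keep the CV-only comparison as a named supportive analysis.
3. Replace the open-ended sparse-data option in SAP 6.3 with a fixed rule, for example to collapse over CV history if a stratum has no subjects in one arm.
4. Add a check restricted to subjects with prospective dose entries.
5. Do not add separate functional-disability strata for the function endpoints; no benefit has been shown.

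**Cost.** No new data are needed. Protocol 9 requires a major change to the primary analysis to appear in a protocol amendment, and Protocol 12 sends amendments to the IRB/IEC, so this is more than a SAP edit. The CV-yes/severe stratum will be small.

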6.3.2.2 Primary Efficacy Endpoint: Sensitivity Analyses

Sensitivity analyses of the primary efficacy endpoint (i.e., pain relief at 2 hours postdose during the DBT Phase) are provided in separate tables.

The RM=F method uses both criteria to classify subjects as failures (see Section 7.5).

Copy Reference Multiple Imputation

The main analysis is repeated using the copy reference multiple imputation approach with $n = 30$ imputations to impute missing headache pain intensity at 2 hours postdose. The fully conditional specification (FCS) method is used with a generalized logit distribution. Covariates may include history of clinically relevant CV disease randomization stratum (yes or no), sex, migraine headache pain intensity at the time of DB study drug dosing (moderate or severe), historical number of moderate to severe migraine attacks per month ($< \text{median}$, $\geq \text{median}$), MBS before DB study drug dosing (nausea, phonophobia, or photophobia), and geographic region (Australia/Europe or North America). First, the RM=F method of handling rescue medication use is applied. Next, missing response status (responder versus failure) in the 2-hour postdose analysis window is imputed for subjects who are not missing any of the covariates (subjects

missing any of the covariates are considered failures). The same statistics as the main analysis are presented, except “n/N”.

Varying Response Rate Imputation

The main analysis is repeated by imputing missing headache pain intensity at 2 hours postdose in each treatment group with varying response rates over the range of 0%, 10%, 20% and 30%. First, the RM=F method of handling rescue medication use is applied. Next, missing response status (responder versus failure) in the 2-hour postdose analysis window is imputed. The following statistics are presented: stratified percentage difference between treatment groups (rimegepant – placebo), ASE, 95% CI, and p-value.

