2 STUDY DESCRIPTION

2.1 Study Design

C4951004 is a multicenter, Phase 4, randomized, double-blind placebo-controlled study, with an Open-Label Extension (OLE) Phase to assess the efficacy and tolerability of rimegepant for the acute treatment of migraine in subjects who are unsuitable for triptan use.

[figure not shown]
The study has 4 phases:

- Screening Phase: Lasts up to 28 days and includes the Screening Visit.
- DBT Phase:
 - Includes the Baseline Visit at which randomization occurs, and DBT EOT Visit.

- Subjects are randomized 1:1 to rimegepant orally dissolving tablet (ODT) 75 mg or matching placebo.
- Randomization is stratified using a Randomization and Trial Supply Management (RTSM) system by history of clinically relevant cardiovascular (CV) disease (yes or no). See Section 2.2.
- After randomization, 1 tablet of study medication is dispensed to subjects to take home for up to 45 days.
- Subjects are instructed by an electronic diary (eDiary) to take 1 tablet of study drug after a migraine attack of moderate or severe headache pain intensity.
- Subjects return to the study site for the DBT EOT Visit either (1) within 7 (\pm 2) days after taking study drug, or (2) within 45 days after randomization otherwise.
- OLE Phase:
 - Subjects who complete the DBT Phase and continue to meet all inclusion/exclusion criteria may enter the OLE Phase, pending review of laboratory test results at the DBT EOT Visit.
 - Subjects may take up to 1 tablet of open-label ODT rimegepant 75 mg per calendar day as needed for acute treatment of migraine for a maximum of 18 doses per month (month is 28 days).
 - Lasts up to 12 weeks, and includes the Week 2, Week 4, Week 8, Week 12, and OLE EOT Visits.
 - All subjects who discontinue early from the OLE Phase should complete the OLE EOT Visit. Otherwise, subjects should complete the Week 12 Visit.
- Follow-Up Phase
 - Lasts up to 2 weeks, and includes the Follow-Up Week 2 Visit primarily for safety assessments. This visit should occur approximately 2 weeks after the Week 12 or OLE EOT Visit.
 - All subjects who enter the OLE Phase should complete the Follow-Up Week 2 Visit (regardless of completing the OLE Phase), except those who discontinue early from the OLE Phase due to withdrawal by subject or lost to follow-up.

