5 SAMPLE SIZE, POWER, AND TYPE I ERROR

It is anticipated that about 90% of the 300 subjects randomized to each treatment group will have a migraine in the allotted time period of the DBT Phase, resulting in approximately 270 subjects evaluable for efficacy in each treatment group.

The sample size calculation is based on pooled results from Phase 3 single-dose migraine studies C4951054 (BHV3000-301), C4951055 (BHV3000-302), and C4951056 (BHV3000-303). Pooled response rates for migraine headache pain relief at 2 hours postdose were 57.9% for rimegepant 75 mg and 43.9% for placebo in these studies.

A total sample size of 540 evaluable subjects (270 per treatment group) will provide approximately 90% power for the primary endpoint of migraine headache pain relief at 2 hours postdose in the DBT Phase. This is based on a chi-square test with a 2-sided alpha level of 0.05, and assumes that the true response rates in the subjects unsuitable for triptan use is equivalent to the overall pooled response rates above.

Type 1 error is controlled using a 2-sided alpha level of 0.05 and hierarchical testing. First, the significance of the primary endpoint is evaluated at the 2-sided alpha level of 0.05 for rimegepant versus placebo. If the primary endpoint is not significant (i.e., $p\text{-value} > 0.05$), then any further tests on key secondary endpoints will have p-values presented only for descriptive purposes. If the primary endpoint is significant (i.e., $p\text{-value} \leq 0.05$), then the key secondary endpoints are tested hierarchically, each at a 2-sided alpha level of 0.05, in the order specified in Section 3.2.2.1. Thus, a key secondary endpoint is tested only if the preceding key secondary endpoint in the hierarchy is determined to be significant (i.e., $p\text{-value} \leq 0.05$). If a test in the hierarchy is not significant, then any further tests on endpoints in the sequence have p-values presented only for descriptive purposes, and no conclusions are drawn from those results.

For testing of other secondary or exploratory endpoints, no attempt is made to adjust for multiplicity. P-values are evaluated at an unadjusted, 2-sided alpha level of 0.05 and presented only for descriptive purposes.

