- Other medication taken to treat headache or aura status (yes or no).
- Headache (Non-migraine) question category: headache (nonmigraine) characteristics parameters (OLE Phase only; see Section 7.4.3)
- MQoL question category: MQoL question parameters at 24 hours postdose (see Section 7.4.4)
- Manual DCF Study medication question category: manual DCF study medication date (see Section 7.4.1.2).

A set of eDiary parameters is defined as those with the same eDiary finding date/time and eDiary completion date/time. The eDiary finding date/time is an internal date/time that is derived by YPrime after the subject answers the first question in the set. The eDiary completion date/time is an internal date/time that is derived by YPrime after the subject answers the last question in the set and saves the results.

Refer to the latest versions of the YPrime C4951004 Data Transfer Specification and eCOA System Requirements Document for additional details.

7.4.1 eDiary Study Medication

7.4.1.1 eDiary Reported Study Medication Date/time

The raw eDiary dataset has a reported study medication date/time parameter (DOSDATIM) with a value that is derived by YPrime from data entered by subjects in study medication parameters the Migraine question category. Date and time are both nonmissing.

Each distinct reported study medication date/time is derived from a distinct set of Migraine question category parameters at the time of prospective or retrospective study drug dosing.

A set of Migraine question category parameters at the time of prospective study drug dosing is defined as one in which (1) there is a “no” response to the eDiary question about already taking study medication, and (2) there is a “yes” response to the eDiary question about confirming that study medication was taken, and (3) eDiary planned time point is missing. The reported study medication date/time is derived by YPrime as the eDiary completion date/time.

A set of Migraine question category parameters at the time of retrospective study drug dosing is defined as one in which (1) there is a “yes” response to the eDiary question about already taking study medication, and (2) eDiary planned time point is missing. Subjects may enter study medication parameters retrospectively on or 1 day before the eDiary finding date as follows:

- During the DBT Phase, subjects must first report taking study medication either “today” or “other”.

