The raw eDiary dataset has a manual DCF study medication date parameter (MDOSDAT) with a value that is entered by YPrime into the Manual DCF Study Medication question category. The data are provided from manual DCFs by sites on days subjects took study medication without using the eDiary.

For each manual DCF date record with distinct eDiary finding date/time, it is assumed that the subject took 1 tablet of study drug for that record.

The manual DCF medication date is not used by the eDiary to collect postdose data.

7.4.2 eDiary Migraine Characteristics

The following migraine characteristics parameters are collected in the Migraine question category (1) at the time of dosing during the DBT Phase and OLE Phases, and (2) at planned

time points postdose from 15 minutes through 48 hours (e.g., 15, 30, 45, 60, and 90 minutes; 2, 3, 4, 6, 8, 24 and 48 hours) during the DBT Phase for a single migraine attack:

- Migraine headache pain intensity (none, mild, moderate, severe)
- MBS (nausea, phonophobia, photophobia). Collected only before dosing (i.e., when there is a “no” response to the question about study medication already taken) during the DBT Phase.
- Nausea status (present, absent)
- Nausea intensity (mild, moderate, severe), if nausea status is present
- Phonophobia status (present, absent)
- Phonophobia intensity (mild, moderate, severe), if phonophobia status is present
- Photophobia status (present, absent)
- Photophobia intensity (mild, moderate, severe), if photophobia status is present
- Functional disability level (normal, mildly impaired, severely impaired, requires bedrest)
- Aura preceding or accompanying headache status (yes, no). Collected only at the time of dosing.

During the OLE Phase, the eDiary also collects migraine headache pain intensity regardless of study drug dosing.

Note that parameters collected “at the time of dosing” or without dosing in the Migraine question category have missing planned time point (see Section 7.4.1.1).

During the DBT Phase, the eDiary allows subjects to report 1 set of migraine characteristics parameters per planned time point.

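### If MBS is used as a covariate, the copy reference multiple imputation repeats NC=F for subjects who enter their dose after the 2-hour window has closed

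*SAP*

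**What the plan says.** The main analysis of 2-hour pain relief scores missing 2-hour pain as failure (NC=F; SAP 6.3 and 6.3.2.1). SAP 6.1.3 presents the sensitivity analyses of the primary endpoint as using other methods for missing data. SAP 6.3.2.2 specifies two of these, and RM=F is applied first in both.

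In the copy reference multiple imputation, "missing response status (responder versus failure) in the 2-hour postdose analysis window is imputed for subjects who are not missing any of the covariates". A parenthesis then makes subjects who lack a covariate failures. The covariates that may be used are CV stratum, sex, pain intensity at dosing, historical attack frequency, MBS before dosing and geographic region. The list is permissive, not fixed.

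The second analysis imputes all missing 2-hour responses at rates of 0%, 10%, 20% and 30% in each arm and uses no covariates.

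On data capture, SAP 7.4.2 says of MBS: "Collected only before dosing", meaning when the subject answers no to having already taken study medication. SAP 7.4.1.1 defines retrospective dose entry by a yes to that question: "Subjects may enter study medication parameters retrospectively on or 1 day before the eDiary finding date as follows". Table 7 of the SAP closes the 2-hour window just before 2 h 16 min.

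**The concern.** MBS and 2-hour pain can be missing for the same reason. A subject who takes the tablet and opens the eDiary some hours later answers yes to having already dosed, so MBS is not asked, and the 2-hour window has already passed. The rule for missing covariates then assigns failure, exactly as the main analysis does.

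The imputation is there to show whether the primary result depends on NC=F. For late reporters it would not show this, and the reader of the table could not tell. The imputation table omits n/N, and the missing-data table in SAP 6.3.1.2 reports missing pain by arm but does not cover MBS or separate prospective from retrospective entry.

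**Working it through.** **The plan's own figure.** SAP section 5 says: "A total sample size of 540 evaluable subjects (270 per treatment group) will provide approximately 90% power for the primary endpoint". Inputs are the pooled rates, which "were 57.9% for rimegepant 75 mg and 43.9% for placebo in these studies", 270 per arm, and two-sided alpha 0.05. The pooled rate is 0.509. The standard error is √(2 × 0.509 × 0.491 / 270) = 0.0430 under the null and √((0.579 × 0.421 + 0.439 × 0.561) / 270) = 0.0426 under the alternative. Power = Φ((0.140 − 1.96 × 0.0430) / 0.0426) = 90.4%. The stated figure reproduces and does not depend on this point.

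**Can a late reporter be in the analysis set and lack both values?**

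1. A qualifying attack is derived from the eDiary record at the time of dosing (SAP 9.3.1), and SAP 7.4.1.1 allows that record to be retrospective.
2. The DBT efficacy set then needs only one nonmissing efficacy value at any planned time from 15 minutes to 48 hours (SAP 4.1). A subject who enters the dose late and completes a later time point is included.
3. That subject has no MBS (SAP 7.4.2) and no 2-hour pain (Table 7).
4. Of the other covariates, pain intensity at dosing must be present for the attack to qualify, and a missing CV stratum falls back on the RTSM value (SAP 6.2.5.1). MBS is the listed covariate whose absence is built into data collection.

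SAP 6.3.5.1 anticipates missing MBS: it is a failure criterion for MBS freedom.

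**How many.** The documents give no rate of retrospective entry or of missing 2-hour pain. Let *m* be the share of an arm still missing 2-hour response after RM=F, and *r* the share of those who lack MBS. Both are assumptions. Subjects scored as failures and not imputed = 270 × *m* × *r*.

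| *m* | missing per arm | *r* = 10% | *r* = 50% | *r* = 100% |
|---|---|---|---|---|
| 2% | 5.4 | 0.5 | 2.7 | 5.4 |
| 5% | 13.5 | 1.4 | 6.8 | 13.5 |
| 10% | 27.0 | 2.7 | 13.5 | 27.0 |

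**Effect on the treatment difference.** Take the planning rates for observed subjects and, because the imputation copies the reference arm, 43.9% for imputed subjects in both arms. With the same *r* in each arm:

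- rimegepant = (1 − *m*_R) × 57.9 + *m*_R × (1 − *r*) × 43.9
- placebo = (1 − *m*_P) × 43.9 + *m*_P × (1 − *r*) × 43.9

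The part of the difference that depends on *r* is (1 − *r*) × 43.9 × (*m*_R − *m*_P).

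- Balanced missingness: this term is zero. The difference is 0.95 × 14.0 = 13.3 points at 5% missing and 0.90 × 14.0 = 12.6 at 10%, for every *r*.
- 8% rimegepant, 3% placebo: all imputed, 56.8 − 43.9 = 12.9; all failures, 53.3 − 42.6 = 10.7.
- 3% rimegepant, 8% placebo: all imputed, 57.5 − 43.9 = 13.6; all failures, 56.2 − 40.4 = 15.8.

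The gap in each unbalanced case is 43.9 × 0.05 = 2.2 points. The all-failures value is the NC=F result, so the rule removes a fraction *r* of the movement the imputation would otherwise show. At *r* = 50% the two cases give 11.8 and 14.7.

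**The case against.** There is a good case that this matters little, and most of it stands.

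- MBS is optional in the list. If it is not chosen, this mechanism disappears. What remains is an open list whose final content decides who is imputed.
- Retrospective entry should be the exception. The protocol's Table 1 and section 4.3.2 require the pre-dose eDiary assessments before the tablet is taken. A reader might infer that many of the subjects missing 2-hour pain go unimputed; no figure in the documents supports that.
- A reader might take the failure rule to cover anyone with a missing covariate. The sentence is about subjects with missing response status. A retrospective reporter who enters the dose before the window closes can still give 2-hour pain, and a prospective reporter who misses the 2-hour entry has MBS and can be imputed.
- RM=F criterion 2 is applied first, so a subject with missing 2-hour pain and timely evidence of rescue is already a failure under the estimand.
- It would be wrong to infer that late reporters go untested. The varying response rate analysis includes them. It stops at 30%, however, below the 43.9% placebo rate used for planning, so neither analysis gives them a placebo-like response.
- A fall in one arm's response rate is not bias in the comparison. It cancels when missingness is balanced, and an excess on rimegepant makes the rule conservative. Only an excess on placebo favours the drug.

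None of this answers the narrower point: a written rule makes the imputation reproduce the assumption under test for a recognisable group.

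**Conclusion.** The point holds, conditional on MBS being used. For late retrospective reporters not already failures under RM=F, the copy reference imputation repeats NC=F. The number is unknown: 0 to 27 per arm over an assumed 0 to 10% missing, and probably small. The treatment difference does not change under balanced missingness. It changes by up to 2.2 points under an assumed 5-point imbalance with every missing subject lacking MBS, in a direction set by which arm has the excess. These figures rest on the planning rates, a 43.9% imputed rate in both arms and the same *r* in each arm.

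The documents do not support a stronger conclusion that the primary result is biased or that the sensitivity programme as a whole fails. The main analysis, the testing hierarchy and the power are unaffected. The change is still worth making, because arm imbalance in missing data is what this analysis should reveal.

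**What to change.** In SAP 6.3.2.2:

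1. Replace the permissive covariate list with a fixed one.
2. Replace MBS with nausea, photophobia and phonophobia status at dosing. SAP 7.4.2 collects these for prospective and retrospective doses. For a late entry they are recalled, but so is pain intensity at dosing, which is already listed.
3. Delete the clause that scores subjects with a missing covariate as failures, and let the FCS procedure already specified impute any remaining missing covariate. Covariates should not be dropped according to which turn out to be missing.

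A useful addition is a count by arm of subjects missing 2-hour pain, split by prospective and retrospective dose entry. The entry type is already derived for the dosing listing (SAP 6.2.6.1).

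The cost is one SAP edit and a small programming change, with no new data.
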